9.3.2 Exclusion Criteria

1. Prior anticancer treatment within 28 days (or 5 times the half-life, whichever is shorter) or any investigational agent within 30 days prior to the first dose of study drugs. All acute toxicities related to prior treatments must be resolved to Grade ≤ 1 .

2. Subjects must have recovered adequately from any toxicity and/or complications from major surgery prior to starting therapy.
3. Subjects having >1+ proteinuria on urinalysis will undergo 24-hour urine collection for quantitative assessment of proteinuria. Subjects with urine protein ≥ 1 g/24-hour will be ineligible.
4. Gastrointestinal malabsorption, gastrointestinal anastomosis, or any other condition that might affect the absorption of lenvatinib
5. New York Heart Association (NYHA) congestive heart failure of grade II or above, unstable angina, myocardial infarction within the past 6 months, or serious cardiac arrhythmia associated with significant cardiovascular impairment within the past 6 months
6. Prolongation of QTc interval to >480 msec
7. Active hemoptysis (bright red blood of at least 0.5 teaspoon) within 3 weeks prior to the first dose of study drug
8. Active infection (any infection requiring systemic treatment)
9. Subject is known to be positive for Human Immunodeficiency Virus (HIV), Hepatitis B or Hepatitis C
10. Serious nonhealing wound, ulcer, or bone fracture
11. Known intolerance to either of the study drugs (or any of the excipients)
12. History of organ allograft (subject has had an allogenic tissue/solid organ transplant)
13. Biologic response modifiers (eg, granulocyte colony-stimulating factor within 4 weeks before study entry. Chronic erythropoietin therapy is permitted provided that no dose adjustments were made within 2 months before first dose of study treatment.
14. Any medical or other condition which, in the opinion of the investigator, would preclude participation in a clinical study
15. Females who are pregnant or breastfeeding
16. Excluding the primary tumor leading to enrollment in this study, any other active malignancy (except for definitively treated melanoma in-situ, basal or squamous cell carcinoma of the skin, or carcinoma in-situ of the bladder or cervix) within the past 24 months
17. Prior treatment with lenvatinib (no exceptions) or any PD-1, anti-PD-L1, or anti-PD-L2 agent, except:

- the melanoma and NSCLC cohorts, where prior treatment with one anti-PD-1, anti-PD-L1, or anti-PD-L2 agent is allowed.
 - the previously treated renal cell carcinoma subjects (as of Amendment 05) where prior treatment with one regimen containing an anti-PD-1/PD-L1 mAb is required.
18. Has a diagnosis of immunodeficiency or is receiving systemic steroid therapy or any other form of immunosuppressive therapy within 7 days prior to the first dose of study treatment. The use of physiologic doses of corticosteroids (up to 7.5mg/d of prednisone or equivalent) may be approved after consultation with the sponsor.
19. No active autoimmune disease that has required systemic treatment in past 2 years (ie, with use of disease modifying agents, corticosteroids or immunosuppressive drugs). Replacement therapy (eg, thyroxine, insulin, or physiologic corticosteroid replacement therapy for adrenal or pituitary insufficiency, etc.) is not considered a form of systemic treatment.
20. Has a history of (non-infectious) pneumonitis that required steroids, or current pneumonitis
21. Has received a live-virus vaccination within 30 days of planned treatment start. Seasonal flu vaccines that do not contain live virus are permitted.

9.3.3 Removal of Subjects From Therapy or Assessment

As of Amendment 09, the Follow-Up Period will consist of the Off-Tx Visit. No further visits will be conducted. The sponsor has decided to terminate survival follow-up for all subjects currently in survival follow-up.

Survival follow-up data will no longer be collected after the Off-Tx Visit and after 30 days from the last dose of study drugs.

The investigator may discontinue treating a subject with study treatment or withdraw the subject from the study at any time for safety or administrative reasons. The subject may decide to discontinue study treatment or withdraw from the study at any time for any reason. The reason for discontinuation will be documented. If a subject discontinues study treatment, the subject will enter the Follow-Up Period and complete protocol-specified off-tx visits, procedures, and survival follow-up unless the subject withdraws consent. The investigator should confirm whether a subject will withdraw from study treatment but agree to continue protocol-specified, off-tx study visits, procedures, and survival follow-up, or whether the subject will withdraw consent. If a subject withdraws consent, the date will be documented in the source documents. The Discontinuation From Treatment CRF page will be completed indicating the primary reason for discontinuation and all other reason(s) contributing to the subject's discontinuation from treatment. In addition, the date of last dose of study drug(s) will be recorded on the Study Drug Dosing CRF page.

During the Follow-Up Period, subjects who have discontinued study treatment without progression should have disease assessments until disease progression is documented or another anticancer therapy is initiated.

All subjects will be followed for survival until death, except where a subject withdraws consent or the sponsor chooses to halt survival follow-up after completion of the primary study analysis. As of Amendment 09, survival follow-up data will no longer be collected.

9.4 Treatments

9.4.1 Treatments Administered

9.4.1.1 Lenvatinib

Lenvatinib will be administered with water orally once a day (with or without food) in 21-day cycles at approximately the same time each day. Treatment cycles will be counted continuously regardless of dose interruptions. On (D1) of each cycle, it will be administered approximately 1 hour after completion of pembrolizumab administration.

9.4.1.1.1 CRITERIA FOR INTERRUPTION OF TREATMENT, DOSE REDUCTION AND RESUMPTION OF TREATMENT

Lenvatinib dose reduction and interruption for subjects who experience lenvatinib-related toxicity will be in accordance with the guidelines provided in Table 2. Once the dose has been reduced, it may not be increased at a later date.

For management of hypertension and proteinuria, refer to main protocol text for instructions before consulting the table below, as appropriate. (See Table 3 for dose reductions. Any dose reduction below 4 mg/day must be discussed with the sponsor. Once the dose has been reduced, it cannot be increased at a later date.) Dose reductions of lenvatinib in Phase 2 occur in succession starting at the RP2D dose identified in Phase 1b.

Table 2 Dose Modifications for Lenvatinib Treatment-Related Toxicity

Lenvatinib Treatment-Related Toxicity ^{a,b}	During Therapy	Adjusted Dose ^f
Grade 1, Tolerable Grade 2		
	Continue treatment	No change
Intolerable Grade 2^{c,d} and Grade 3^g		
First occurrence	Interrupt lenvatinib until resolved to tolerable Grade 2 or Grade 0-1	Reduce lenvatinib by one dose level ^b
Second occurrence (same toxicity or new toxicity)	Interrupt lenvatinib until resolved to tolerable Grade 2 or Grade 0-1	Reduce lenvatinib by one more dose level
Third occurrence (same toxicity or new toxicity)	Interrupt lenvatinib until resolved to tolerable Grade 2 or Grade 0-1	Reduce lenvatinib by one more dose level
Fourth occurrence (same toxicity or new toxicity)	Interrupt lenvatinib until resolved to tolerable Grade 2 or Grade 0-1	Reduce lenvatinib by one more dose level

Grade 4^g: Discontinue lenvatinib
--

- a. An interruption of lenvatinib treatment for more than 21 days (due to lenvatinib treatment-related toxicities) will require a discussion with the sponsor before treatment can be resumed.
- b. Excluding alopecia. Initiate optimal medical management for nausea, vomiting, hypothyroidism, hypertension and/or diarrhea prior to any lenvatinib interruption or dose reduction. For treatment-related hypertension, refer to Management of Hypertension (Section 9.4.1.1.2) for dose modification guidelines.
- c. Applicable only to Grade 2 toxicities judged by subject and/or physician to be intolerable.
- d. Obese subjects with weight loss do not need to return to the baseline weight or 10% of baseline weight (ie, Grade 1 weight loss). These subjects will restart the study drug(s) at a lower dose once their weight remains stable for at least 1 week and they reached the normal body mass index (BMI) (if the weight loss occurred but it is still above normal BMI, they can restart the study treatment at a lower dose once the weight has been stable for at least 1 week). Normal BMI should be used as the new baseline for further dose reductions.
- e. Excluding laboratory abnormalities judged to be non-life-threatening, in which case manage as Grade 3.
- f. Refer to Table 3 for adjusted dose.
- g. For asymptomatic Grade ≥ 3 elevations of amylase and lipase, the sponsor's medical monitor should be consulted to obtain permission to continue treatment.

General guidelines for holding periods of lenvatinib due to procedures:

For minor procedures, lenvatinib should be stopped 2 days before the procedure and restarted 2 days after, once there is evidence of adequate healing and no risk of bleeding. Needle biopsies (fine needle aspirations and core needle aspiration) are usually considered minor procedures.

For major procedures, lenvatinib should be stopped at least 1 week (5 half-lives) before the procedure and then restarted once there is clear wound healing and no risk of bleeding, but at least 2 weeks after the procedure. It is up to the investigator to determine if it is a major or minor procedure. Usually a major procedure implies general anesthesia.

Table 3 Dose Reduction Recommendations for Lenvatinib Treatment-Related Toxicity

Initial Lenvatinib Dose (mg, QD)	Adjusted Dose To Be Administered (mg, QD)			
	Reduction 1	Reduction 2	Reduction 3	Reduction 4
24	20	14	10	8 ^a
20	14	10	8	4 ^a
14	10	8	4 ^a	

QD = once a day

a. Consult sponsor for further dose reduction recommendations.

9.4.1.1.2 MANAGEMENT OF HYPERTENSION

Hypertension is a recognized side effect of treatment with drugs inhibiting vascular endothelial growth factor (VEGF) signaling. Investigators should therefore ensure that subjects enrolled to receive treatment with lenvatinib have BP of $\leq 150/90$ mm Hg at the time

of study entry and, if known to be hypertensive, have been on a stable dose of antihypertensive therapy for at least 1 week before C1D1. Early detection and effective management of hypertension are important to minimize the need for lenvatinib dose interruptions and reductions.

Antihypertensive agents should be started as soon as elevated BP (systolic BP ≥ 140 mm Hg or diastolic BP ≥ 90 mm Hg) is confirmed on 2 assessments a minimum of 1 hour apart. One BP assessment is defined as the mean value of 3 measurements at least 5 minutes apart. The choice of antihypertensive treatment should be individualized to the subject's clinical circumstances and follow standard medical practice. For previously normotensive subjects, appropriate antihypertensive therapy should be started when systolic BP ≥ 140 mm Hg or diastolic BP ≥ 90 mm Hg is first observed on 2 assessments a minimum of 1 hour apart. For those subjects already on antihypertensive medication, treatment modification may be necessary if hypertension persists. For subjects with hypertension and proteinuria, appropriate therapy, eg, angiotensin-converting enzyme inhibitor or angiotensin-II receptor antagonist, is preferred (Kilfoy, et al., 2009).

Lenvatinib should be withheld in any instance where a subject is at imminent risk to develop a hypertensive crisis or has significant risk factors for severe complications of uncontrolled hypertension (eg, BP $\geq 160/100$ mm Hg, significant risk factors for cardiac disease, intracerebral hemorrhage, or other significant co-morbidities). Once the subject has been on the same hypertensive medications for at least 48 hours and the BP is controlled, lenvatinib should be resumed as described below.

During the Treatment Period, both in the Treatment Phase and in the Extension Phase, subjects with systolic BP ≥ 160 mm Hg or diastolic BP ≥ 100 mm Hg must have their BP monitored on Day 15 or more frequently as clinical indicated until systolic BP has been ≤ 150 mm Hg and diastolic BP has been ≤ 95 mm Hg for 3 consecutive months. If a repeat event of systolic BP ≥ 160 mm Hg or diastolic BP ≥ 100 mm Hg occurs, the subject must resume the Day 15 evaluation until systolic BP has been ≤ 150 mm Hg and diastolic BP has been ≤ 95 mm Hg for 3 consecutive months.

The following guidelines should be followed for the management of systolic BP ≥ 160 mm Hg or diastolic BP ≥ 100 mm Hg confirmed on repeat measurements after 1 hour:

1. Continue lenvatinib and institute antihypertensive therapy for subjects not already receiving antihypertensive medication
2. For those subjects already on antihypertensive medication, dose of the current agent may be increased, if appropriate, or 1 or more agents of a different class of antihypertensive should be added.
3. If systolic BP ≥ 160 mm Hg or diastolic BP ≥ 100 mm Hg persists despite maximal antihypertensive therapy, then lenvatinib administration should be interrupted. It should be restarted at one lower dose level as specified in [Table 3](#) only when systolic BP ≤ 150 mm Hg and diastolic BP ≤ 95 mm Hg and the subject has been on a stable dose of antihypertensive medication for at least 48 hours

- If systolic BP ≥ 160 mmHg or diastolic BP ≥ 100 mmHg recurs on the first dose reduction despite optimal management of hypertension with antihypertensive medications (either by dose increase or the addition of a different class of antihypertensive), then lenvatinib administration should be interrupted. It should be restarted at an additional dose reduction as specified in [Table 3](#) only when systolic BP ≤ 150 mmHg and diastolic BP ≤ 95 mmHg and the subject has been on a stable dose of antihypertensive medication for at least 48 hours.
- If systolic BP ≥ 160 mmHg or diastolic BP ≥ 100 mmHg recurs on the second dose reduction despite optimal management of hypertension with antihypertensive medications (either by dose increase or the addition of a different class of antihypertensive), then lenvatinib administration should be interrupted. It should be restarted at a third dose reduction as specified in [Table 3](#) only when systolic BP ≤ 150 mmHg and diastolic BP ≤ 95 mmHg and the subject has been on a stable dose of antihypertensive medication for at least 48 hours.

The following guidelines should be followed for the management of Grade 4 hypertension (life-threatening consequences):

- Institute appropriate medical management
- Discontinue study drug

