 - a. At least 1 lesion of ≥ 10 mm in the longest diameter (LDi) for a non-lymph node or ≥ 15 mm in the short-axis diameter for a lymph node that is serially measurable according to irRECIST using computerized tomography/magnetic resonance imaging (CT/MRI).
 - b. Lesions that have had external beam radiotherapy or loco-regional therapies such as radiofrequency) ablation must show subsequent evidence of substantial size increase to be deemed a target lesion.

4. Subjects must have an Eastern Cooperative Oncology Group (ECOG) Performance Status (PS) of 0 to 1.
5. Adequately controlled blood pressure (BP) with or without antihypertensive medications, defined as BP $\leq 150/90$ mmHg at screening and no change in antihypertensive medications within 1 week prior to the C(C) 1 D1.
6. Adequate renal function defined as creatinine $\leq 1.5 \times$ (upper limits of normal (ULN) or calculated creatinine clearance ≥ 40 mL/min per the Cockcroft and Gault formula with creatinine levels $> 1.5 \times$ ULN.
7. Adequate bone marrow function:
 - Absolute neutrophil count (ANC) $\geq 1500/\text{mm}^3$ ($\geq 1.5 \times 10^3/\mu\text{L}$)
 - Platelets $\geq 100,000/\text{mm}^3$ ($\geq 100 \times 10^9/\text{L}$)
 - Hemoglobin ≥ 9.0 g/dL
8. Adequate blood coagulation function as evidenced by an International Normalized Ratio (INR) ≤ 1.5 .
9. Adequate liver function as evidenced by bilirubin ≤ 1.5 times the ULN and alkaline phosphatase (ALP), alanine aminotransferase (ALT), and aspartate aminotransferase (AST) $\leq 3 \times$ ULN (in the case of liver metastases $\leq 5 \times$ ULN). In case ALP is $> 3 \times$ ULN (in the absence of liver metastases) or $> 5 \times$ ULN (in the presence of liver metastases) AND the subject also is known to have bone metastases, the liver specific ALP isoenzyme must be separated from the total and used to assess the liver function instead of the total ALP.
10. Males or females age ≥ 18 years at the time of informed consent.
11. Subjects with known brain metastases will be eligible if they have completed the primary brain therapy (such as whole brain radiotherapy, stereotactic radiosurgery or complete surgical resection) and if they have remained clinically stable, asymptomatic and off of steroids for at least 28 days before starting study treatment.

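### Protocol 9.4.1.1.2 gives opposite lenvatinib instructions for an untreated subject with confirmed BP at or above both 160 systolic and 100 diastolic, and states no precedence (minor wording error)

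*Protocol*

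**What the plan says.** Protocol 9.4.1.1.2 (Management of Hypertension) contains both instructions.

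- **The withhold paragraph.** It begins "Lenvatinib should be withheld in any instance where a subject is at imminent risk to develop a hypertensive crisis". The same sentence extends the hold to a subject who "has significant risk factors for severe complications of uncontrolled hypertension (eg, BP $\geq 160/100$ mm Hg"; the examples then continue with cardiac risk factors, intracerebral hemorrhage and other significant co-morbidities. Lenvatinib resumes once the subject has spent at least 48 hours on unchanged medication with BP controlled, in the manner set out further down the section.
- **The numbered list.** Its lead-in starts "The following guidelines should be followed for the management of systolic BP" and sets the threshold at systolic ≥160 or diastolic ≥100 mm Hg, confirmed on repeat after 1 hour. Item 1 reads "Continue lenvatinib and institute antihypertensive therapy for subjects not already receiving antihypertensive medication". Item 2 covers subjects already on antihypertensives, by raising the dose or adding an agent. Item 3 applies if BP at that level "persists despite maximal antihypertensive therapy, then lenvatinib administration should be interrupted", with restart at a lower dose level.

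Three other places bear on the choice. The section states its aim: "Early detection and effective management of hypertension are important to minimize the need for lenvatinib dose interruptions and reductions". Footnote b to Table 2 (9.4.1.1.1, repeated in the Synopsis) asks for optimal medical management of hypertension before any interruption or reduction of lenvatinib, then refers to 9.4.1.1.2. The Synopsis text on dose modification and section 9.5.1.5.4 only send the reader to the main text or to 9.4.1.1.2.

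**The concern.** A dosing rule should give one answer for one subject. Here a site that follows the withhold paragraph to the letter stops lenvatinib, and a site that follows item 1 of the list carries on. Both are following the same section, and the study allows up to 25 sites. What is at stake is consistency of dosing in a small group of subjects. The same paragraph also leaves the resumption dose unstated after such a hold, because every restart described below it is at a reduced dose.

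**Working it through.** The documents give no figure on this point to reproduce. The check is to apply both texts to one subject, see whether that subject can occur, and then size the difference.

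**Step 1. Apply both texts.** Take BP 165/105 mm Hg, confirmed after 1 hour, no antihypertensive in use, no other risk factor.

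| Text in 9.4.1.1.2 | Condition met? | Action |
|---|---|---|
| Withhold paragraph, read literally | Yes: BP is above the 160/100 example, one item in a list joined by *or* | Withhold |
| Numbered list, item 1 | Yes: at or above both limits, untreated | Continue and start therapy |

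**Step 2. Find the limits of the conflict.**
- At 165/90 the list still applies, because either limit is enough. The 160/100 example is not clearly met, so the explicit conflict needs both values raised.
- For subjects already on antihypertensives, items 2 and 3 only imply continuation, so the instructions are not explicitly opposed.

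**Step 3. Can the case occur?**
- Inclusion Criterion 5 (9.3.1) asks for "Adequately controlled blood pressure (BP) with or without antihypertensive medications", at ≤150/90 mm Hg at screening, so untreated subjects may enter.
- "Antihypertensive agents should be started as soon as elevated BP" (systolic ≥140 or diastolic ≥90 mm Hg) is confirmed. The case therefore needs a rise from below 140/90 to 160/100 or more between checks.
- Table 9 schedules vital signs on Days 1 and 15 of Cycle 1, nominally 15 − 1 = 14 days apart. Later checks are on Day 1 of each cycle, up to 21 days apart if Day 15 monitoring is only for subjects already flagged.

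So the case is possible, but it needs a quick rise.

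**Step 4. Look for a precedence rule.** 9.4.1.1.1 and the Synopsis put the main text ahead of Table 2. Neither ranks the withhold paragraph against the list. Footnote b is a real sequencing instruction (medical management first), but it does not mention the withhold paragraph and it defers to the section where the conflict lies.

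**Step 5. Size the difference.** Inputs: 20 mg once daily in Phase 2 (9.1), 21-day cycles, an 8-cycle Treatment Period (9.1.2.1) and a hold of at least 48 hours (9.4.1.1.2). Assume that day's dose has not been taken and that the first antihypertensive controls BP at once.

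- Doses missed under item 1: 0.
- Doses missed under the withhold paragraph: 48 h ÷ 24 h = 2, or 2 × 20 = 40 mg.
- Share of one cycle: 2/21 = 9.5%; in mg, 40/(21 × 20) = 40/420 = 9.5%.
- Share of eight cycles: 8 × 21 = 168 doses; 2/168 = 1.2%; in mg, 40/(168 × 20) = 40/3360 = 1.2%.

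Since 48 hours is a minimum, slower control of BP would mean more missed doses.

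**The case against.** The best counter-argument is that the parenthesis describes a high-risk subject and is not a set of stand-alone triggers. If every item triggered a hold alone, a normotensive subject with cardiac risk factors could never take lenvatinib. Exclusion Criterion 5 bars only specified cardiac conditions, so such subjects can enrol. On this reading the 165/105 subject with no other risk factor falls under item 1 only. The cross-reference for resumption also ties the paragraph to the list, where item 3 carries the same 48-hour condition. Footnote b puts medical management before any interruption.

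Much of this stands. It shows that continuation is the intended action. It does not remove the conflict, because the wording does not require that reading: BP ≥160/100 appears as one alternative among several, under a sentence that applies in any instance. Sharing a restart condition with item 3 does not cancel an instruction to stop.

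It is also fair to say that the effect is small and the case unusual, and that under Amendment 09 few or no subjects may still be in the 8-cycle Treatment Period. The section's rule for monitoring BP at this threshold covers the Extension Phase too, so the point remains live for anyone still on study lenvatinib.

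**Conclusion.** Wrong as written, and minor. For an untreated subject with confirmed BP at or above both limits and no other risk factor, the section says both to stop and to continue lenvatinib. Context favours continuing; no text says so. The cost of the literal reading is about 2 doses per occurrence, under the assumptions in the working. The number of occurrences cannot be derived from the documents.

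Three stronger conclusions are tempting but unsupported.

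- *Subjects are left at risk.* Under either text antihypertensives are started and BP monitoring continues, and Grade 4 hypertension means discontinuation.
- *The literal hold forces a permanent dose reduction.* The restarts described are all at lower doses, and 9.4.1.1.1 bars later increases. But those restarts are written for BP that persists or recurs despite treatment. The resumption dose after a hold under the withhold paragraph is unstated, so no reduction can be claimed.
- *The efficacy results or sample size are affected.* No statistical figure in the protocol or SAP depends on this wording.

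**What to change.** Reword the withhold paragraph and remove BP ≥160/100 mm Hg as an example that stands alone. For instance:

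*Withhold lenvatinib if a hypertensive crisis is imminent, or if systolic BP is ≥160 mm Hg or diastolic BP is ≥100 mm Hg in a subject who also has a significant cardiac risk factor, intracerebral hemorrhage or another significant co-morbidity. Items 1 to 3 below govern all other subjects with confirmed BP at that threshold. After a hold under this paragraph, resume at [dose to be specified by the sponsor].*

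The BP condition must attach to the co-morbidities. Deleting only the BP example and giving the paragraph an override would let a co-morbidity alone trigger a hold with explicit priority over the list.

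Table 2 footnote b, the Synopsis and 9.5.1.5.4 need no change. The cost is one paragraph at the next amendment, or a site memo until then, with no new procedures or data. The resumption dose is a clinical choice for the sponsor.
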